The investigators and study coordinator will communicate weekly and meet at least twice monthly to discuss and address potential problems, ensure timely communication with the IRB if needed, and monitor study accrual. Two forms of recruitment materials will be generated: 1) patient-facing advertisement and recruitment material that are eye-catching and written to an 8th-grade reading level. Content will describe the study purpose, key eligibility criteria, and contact information for the study coordinator. Materials will be posted in WCI clinic and community areas where patients and caregivers are likely to be circulating; i.e., cafeteria, lobby, waiting areas and clinic rooms; 2) provider-targeted correspondence summarizing key study objectives and clearly outlining eligibility criteria, period of enrollment, study coordinator contact information, and highlighting the ongoing nature of the study. These materials will be distributed to WCI faculty and hematology/oncology medical fellows. The study coordinator will contact potentially eligible participants through participant self-referral or referral by the oncology team. The coordinator will screen the electronic health record to confirm eligibility, then schedule a time to meet with the participant. INCLUSION/EXCLUSION CRITERIA: Subjects will be considered for enrollment in this study if able to provide consent, at least 18 years old, and report moderate-severe pain (at least 4 out of 10 where pain is rated on a Likert scale between zero and 10) in the previous 7 days as a result of either cancer or cancer treatment. Palliative care consultation and/or referral to palliative care is not required for eligibility or participation. Additionally, participation will not be limited by whether subjects are receiving specific cancer-directed therapies at the time of enrollment. Subjects will be excluded if they already use VR for personal use, have intractable nausea/vomiting, history of motion sickness, history of seizures or epilepsy, have cranial structure abnormalities that prevent use of VR headset, or are currently enrolled in a palliative care or pain management study. Subjects will also be excluded if they have limited vision or vision defects that are not corrected with prescription eyeglasses, or if participants are unable or do not wish to wear required corrective eyeglasses with the VR headset. Informed consent will be conducted before enrolling each patient.

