Because of the nature of the compared interventions, subjects and researchers cannot be blinded to intervention. Our primary outcome measure will determine the impact of VR on self-reported pain score in the last week (numeric rating scale, collected weekly). Self-reported pain experience remains the standard for clinical pain research. Secondary outcomes will measure pain interference (PROMIS Pain Interference Short Form, collected weekly), as-needed opioid use for patients taking opioid analgesics at the time of enrollment (self-reported using medication administration form), satisfaction with VR intervention and overall pain management (collected weekly), and survey of preferences for VR thematic content (collected after Week 4).

Following consent, subjects will complete baseline outcome assessments including self-reported pain score in the last week, the PROMIS Pain Interference Short Form, as-needed opioid use in the last week if applicable, and satisfaction with overall pain management. Subjects will then be provided with a VR headset and paired Touch controllers to bring home for the duration of the study and instructions on the frequency of use for each week. A member of the research will educate the patient on the technology and assure comfort with use. The research study coordinator will contact patients by phone at the end of each week to confirm dates and duration of use as specified by the study protocol, collect self-reported pain score in the last week, the PROMIS Pain Interference Short Form, as-needed opioid use in the last week if applicable, and satisfaction with the VR intervention and overall pain management. Additionally, participants will be surveyed on preferences for VR thematic content at the end of Week 3.

Participants will be monitored for adverse effects and harm for the duration of the study. Although well tolerated in previous studies of patients with cancer and advanced heart failure, potential risks may include dizziness, nausea, eye strain, and loss of confidentiality if data security is breached. Participants are instructed to only utilize the VR device while in a seated or reclined position and to never use the device when standing or ambulating due to the risk of potentially serious injury from falling.

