Descriptive analyses will be performed to summarize baseline characteristics, including initial pain measures from self-report pain rating scale and PROMIS Pain survey. Preferences for VR thematic content and satisfaction with VR intervention will also be summarized. Summary statistics include frequency (%) for categorical variables and mean, standard deviations, median and IQR (1st and 3rd quartile) for continuous variables. Paired t-test or Wilcoxon sign rank test will be used to compare each

time point (end of weeks 1, 2, and 3) to the baseline (beginning of week 1) regarding pain score and PROMIS survey outcomes. Linear mixed-effects model will be used to assess the trend of pain score over the study period controlling for pain medication usage and other covariates (e.g., age, sex).

Data Collection Plan:

Time of Data Collection	Method of Data Collection+	Data Elements Collected
Beginning of Week 1 (Time of Enrollment)	Patient Survey (all patients)	 Self-reported pain score PROMIS Pain Interference Short Form As-needed opioid use* Satisfaction with overall pain management
End of Week 1	Patient Survey (all patients)	 Self-reported pain score PROMIS Pain Interference Short Form As-needed opioid use* Satisfaction with VR intervention and overall pain management
End of Week 2	Patient Survey (all patients)	 Self-reported pain score PROMIS Pain Interference Short Form As-needed opioid use* Satisfaction with VR intervention and overall pain management
End of Week 3	Patient Survey (all patients)	 Self-reported pain score PROMIS Pain Interference Short Form As-needed opioid use* Satisfaction with VR intervention and overall pain management Preferences for VR thematic content

* Data collected for patients receiving as-needed opioid analgesics at the time study enrollment

+ Patient survey administered by Research Coordinator by phone, data entered into Tonic Health

DATA SHARING

Data collected over the course will include summary findings of N = 60 enrolled participants. Per MHRI policy and in full alignment with NIH policy, all data compiled from this and future projects related to data collected in this study will be available upon request by any academic or government researcher, with data shared via existing pathways built to ensure transparency but protect participants. As part of the NIH data sharing directive, de-identified data from this study will be transferred to the PCRC De-Identified Data Repositories.

RECORD RETENTION

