	In the past 7 days	Never	Rarely	Sometimes	Often	Always
PAININ26	How often did pain keep you from socializing with others?		2 2	□	4	5

© 2008-2012 PROMIS Health Organization and PROMIS Cooperative Group

Page 1 of 1

Phone Script for Weekly Follow-Up Calls

Hello, my name is _______. I would like to speak with [*participant name*]. To ensure I am speaking with the correct individual, would you mind confirming your date of birth and zip code? *Confirm identity using two identifiers, i.e. date of birth and zip code.* Thank you! I am the research coordinator for the Virtual Reality Study you are participating in through the Washington Cancer Institute at MedStar Washington Hospital Center. We had scheduled a call at this time to collect information about your experience with the virtual reality headset and experience with pain in the last week; is this alright time to speak? *If patient says yes, proceed with survey tool. If patient says no, coordinate a time to follow up.*

- *If Yes:* Thank you! I will go through the survey questions with you now. The questions should take approximately 5 to 10 minutes to complete. Please stop me at any time if you need more time or have questions about the survey. *Administer survey tools*.
- *If No:* Thank you for letting me know, what would be a better time to give you a call? The questions should take approximately 5 to 10 minutes to complete. Is this still the best number to reach you at?

At the end of the survey. Thank you for your responses! Do you have any questions or concerns you would like to discuss with me? Please note that you can contact us at any time if issues arise later on. You have completed Week X of the study and have X week(s) remaining. We would like to remind you that for Week X, you will be using the VR headset for 10 minutes (*once a day/twice a day/as often as you wish*). We will give you another call at the end of the week to review the survey questions. What would be a good time for me to call you at the end of the week? *Confirm day 7 and follow-up time as well as best contact information*.

Thank you! That concludes our follow-up call for Week X. We will contact you again at scheduled date and time, however you may reach out to us at any point if you have questions or concerns. Confirm participant has contact information for research team. Have a good morning/afternoon/evening.

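### From Week 1 the call script names the headset before the survey and the satisfaction item names it before PROMIS; baseline does neither, and the mode of the baseline survey is stated inconsistently.

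*Combined protocol and SAP*

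**What the plan says.** **Baseline.** In STUDY DESIGN AND METHODS the recruitment text reads "The coordinator will screen the electronic health record to confirm eligibility, then schedule a time to meet with the participant". The outcome text then reads "Following consent, subjects will complete baseline outcome assessments including self-reported pain score in the last week", followed by "Subjects will then be provided with a VR headset and paired Touch controllers to bring home for the duration of the study". Baseline therefore comes after consent and before the participant has the device. None of the items on the Baseline/Time of Enrollment form mentions VR.

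**Weeks 1 to 3.** The coordinator is to "contact patients by phone at the end of each week to confirm dates and duration of use as specified by the study protocol" and to collect the outcomes. The Phone Script for Weekly Follow-Up Calls tells the participant that the call is to "collect information about your experience with the virtual reality headset and experience with pain in the last week"; the survey is administered only after that. On the follow-up forms the satisfaction item (item 3) adds a clause on use of the headset. PROMIS Pain Interference is item 4.

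**Mode.** In the Data Collection Plan table under DATA ANALYSIS, the column headed "Method of Data Collection" carries a footnote: "Patient survey administered by Research Coordinator by phone, data entered into Tonic Health". The mark is on the column header, so it covers the enrolment row as well as the three follow-up rows. No exception is made for baseline.

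**The concern.** The planned tests compare each of Weeks 1, 2 and 3 with baseline, by paired t-test or Wilcoxon test, for pain and PROMIS. The study is non-randomized, unblinded and single-arm. Anything in the way answers are obtained that is absent at baseline and present at every follow-up enters all of these differences in full. Being reminded of the headset just before rating pain, or asked about satisfaction with care that includes the headset just before PROMIS, could move the answers without any change in pain. If baseline is also taken face to face and follow-up by phone, interview mode changes at the same moment.

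The planned mixed model, which adjusts for pain medication use and covariates such as age and sex, does not remove a shift that coincides with the start of VR. The protocol also intends to use the observed effect and variance to size a larger study, so a spurious shift would carry forward into that calculation.

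**Working it through.** **1. What changes between baseline and follow-up, and what does not.**

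| Feature | Baseline | Weeks 1 to 3 |
|---|---|---|
| Headset provided | Not yet | Yes |
| Headset named before the survey starts | No such script given | Yes, in the opening of the call script |
| Pain item | Item 1, no VR wording | Item 1, same wording |
| Satisfaction item | Item 3, no VR wording | Item 3, VR clause added |
| PROMIS | Item 4, after satisfaction | Item 4, after satisfaction |
| Who collects the data (DATA COLLECTION) | Study coordinator | Study coordinator |
| Mode | Meeting implied by the methods text; phone by the table footnote | Phone |

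(The Week 3 form prints its first four items again as items 5 to 8. Nothing here depends on that.)

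For pain, the documented change is therefore the opening line of the call. For PROMIS it is the opening line plus the VR clause in the item just before it. A change of mode is possible for both, but is not established.

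**2. Baseline mode.** A scheduled meeting, then consent, baseline, and handover of a device to take home, with phone contact described only for the end of each week, reads as an in-person baseline. The table footnote, taken literally, makes it a phone survey. Both cannot describe the same assessment.

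**3. Illustration of size.** The plan gives no SD, no effect size and no estimate of any reporting shift, so there is no figure of its own to reproduce. Inputs:

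- n = 60, with 30 as the stated fallback (both from the protocol).
- SD of the change in pain = 2 points, range 1.5 to 2.5 (assumption).
- Favourable reporting shift b = 0.2, 0.3 or 0.5 points on the 0 to 10 scale (assumption).
- True VR effect zero; two-sided paired t-test at 0.05 (the level is an assumption).

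Standard error = SD/√n = 2/√60 = 0.258. Noncentrality = b/SE: 0.2/0.258 = 0.77, 0.3/0.258 = 1.16, 0.5/0.258 = 1.94. The critical value with 59 degrees of freedom is 2.001. The chance of a false significant benefit is the probability that a noncentral t exceeds this value:

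| n | SD of change | b = 0.2 | b = 0.3 | b = 0.5 |
|---|---|---|---|---|
| 60 | 1.5 | 17% | 33% | 72% |
| 60 | 2.0 | 11.5% | 20.7% | 47.8% |
| 60 | 2.5 | 9% | 15% | 33% |
| 30 | 2.0 | 8% | 12% | 26% |

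With b = 0 the figure is 2.5% in every row. These are chances per comparison; the plan makes three such comparisons for each outcome.

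**The case against.** The strongest reply is that the primary outcome is largely protected. The pain question has the same wording at all four assessments and comes first on every form, so what is left for pain is one introductory phrase. The arithmetic shows only what an assumed shift would do. No document gives its size or says that it would favour VR, and the same calculation could be attached to any suspected bias in a single-arm study. The protocol is open about being an unblinded pilot, and editing a script will not remove participants' expectations. All of this stands, and it limits the weight of the point. It does not remove the difference in context, which is in the documents and can be avoided.

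Four stronger readings are tempting, and the documents do not support them:

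- **That the mode of assessment does change when VR starts.** An in-person baseline is an inference from the methods text. The only explicit statement of mode, the table footnote, says phone. The instruction on the PROMIS form to mark boxes does not help, because the same form is used at every assessment.
- **That baseline is free of VR context.** Participants have by then consented to a VR study. What can be said is that they have no headset yet and that the items do not mention one.
- **That pain is asked straight after a compliance check.** The methods text lists confirmation of VR use first, but that list is not an interview order: it puts PROMIS before opioid use and satisfaction, while the forms put it after them. The script places no VR-use check before the survey, and no form has a VR-use item.
- **That the position of satisfaction ahead of PROMIS is new at follow-up.** It is the same at baseline. Only the VR clause is new.

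**Conclusion.** The concern holds in a limited form. The context of questioning changes when VR starts: the headset is named before the survey at every follow-up, and the satisfaction item ahead of PROMIS gains a VR clause. The baseline mode is inconsistent between the methods text and the data collection table; if baseline is in fact face to face, mode changes at the same point. With no control group, any resulting reporting shift is fully confounded with VR in the planned baseline comparisons of pain and PROMIS.

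The size and direction of such a shift are unknown. The range of about 12% to 48% for a false significant benefit rests on n = 60, an assumed SD of change of 2 points and an assumed favourable shift of 0.2 to 0.5 points. It shows sensitivity and does not estimate the bias. The exposure is smaller for pain than for PROMIS, because the pain item is unchanged and comes first. The case for acting is that the asymmetry is avoidable at very little cost.

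**What to change.** 1. Reconcile STUDY DESIGN AND METHODS with the footnote to the Data Collection Plan table, and state how, where and by whom baseline is taken.
2. Have the coordinator read the same scripted items at all four assessments. If baseline is in person, the items are read aloud at the enrolment meeting before the headset is shown.
3. Remove the headset from the opening line of the follow-up script.
4. Ask pain, as-needed opioid use and PROMIS first, and only then satisfaction, VR use and content preferences.

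The cost is a small edit to the script and a reordering of the forms. Reading aloud at the meeting adds no contact; a separate baseline phone call between consent and handover could add one, so reading aloud is the cheaper route if the meeting stands. These changes do not remove expectation effects, which stay with the uncontrolled, unblinded design and should be acknowledged when results are reported.

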⁴ Griffin KH, Nate KC, Rivard RL, Christianson JB, Dusek JA. Referrals to integrative medicine in a tertiary hospital: findings from electronic health record data and qualitative interviews. BMJ Open. 2016 Jul 25;6(7):e012006. doi: 10.1136/bmjopen-2016-012006.

⁵ Nahin RL, Barnes PM, Stussman BJ. Insurance coverage for complementary health approaches among adult users: United States, 2002 and 2012. NCHS data brief, no 235. Hyattsville, MD: National Center for Health Statistics. 2016.

⁶Fletcher CE, Mitchinson AR, Trumble EL, Hinshaw DB, Dusek JA. Perceptions of other integrative health therapies by Veterans with pain who are receiving massage. J Rehabil Res Dev. 2016;53(1):117-26. doi: 10.1682/JRRD.2015.01.0015.

seem to modulate pain by reducing the level of attention paid to noxious stimuli, thereby suppressing transmission of painful sensations to the cerebral cortex. ^{10,11} When used in addition to usual care (opioid analgesics, with or without non-interactive distraction therapies), VR has been shown to provide clinically and statistically significant reduction in subjective pain score ratings. ^{12,13} The immersive nature of VR makes it a more engaging form of distraction therapy compared to playing a video game or listening to music (e.g. rather than watching a video of a beach, one visually and acoustically experiences being at the beach). Additionally, VR is becoming increasingly portable and affordable with growing availability of thematic content such that patients may select VR experiences that interest them.

Despite growing evidence to the benefit of VR for pain management, no research has yet elucidated its role in outpatients with cancer-related pain.

PURPOSE

The purpose of this research project is to evaluate the impact of virtual reality therapy on mitigating moderate to severe cancer pain in outpatients.

AIMS and HYPOTHESES

Specific Aim 1: To collect and compare pilot data on the impact of a VR intervention against standard care (pre-enrollment analgesic regimen) on pain management measures for outpatients with cancer who have a baseline pain self-rated at least 4/10 (0=no pain, 10=worst pain).

Hypothesis 1: Patients with cancer receiving a virtual reality (VR) intervention will have significantly larger improvements in self-reported pain scores, satisfaction with pain management, lower distress, greater well-being, and lower as-needed opioid use compared to their baseline.

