This is a non-randomized, unblinded dose-titration study. After consenting to participate, in addition to usual pharmacologic pain management, participants will receive 1 week of VR daily for 10 minutes per session, then 1 week of VR twice a day for 10 minutes per session, then 1 week of VR use as desired by the participants.

VR sessions will be administered using the Facebook (Facebook Inc., Menlo Park, CA) Meta Quest 2 VR and Touch controllers. This equipment was selected because it is portable, has built in audio, and has clear graphics at a lower price than VR setups that require a computer to generate graphics. The headset has an optional eyeglass spacer to allow participants to wear corrective eyeglasses during the

VR session if appropriate. The hand controllers facilitate immersive, interactive VR experiences. Of note, we considered using smartphone-based VR technology for this study; however, although technology continues to evolve, smartphone-based VR technology has not yet evolved enough to provide an adequately immersive VR experience to assure accurate results. The VR software, Nature Treks VR application (https://naturetreksvr.com) that features ten non-violent, nature-based experiences in peaceful environments (e.g. forest, river, beach, etc.) that can be played in a seated or fixed position. A Facebook/Meta account is currently required to login to the Quest 2 device; to protect patient privacy and ensure access to the Nature Treks application, the research team will activate the device with a dummy Meta account that does not contain any patient-specific information or payment information prior to distribution to participants. Participants will be provided with information on resetting the device to factory settings at the end of the study period if they wish to remove the dummy account and access the device using a personal Meta account for future, personal use of the device. Participants will not be prevented from searching for or downloading other VR programs onto the device during the study period, but will not be able to purchase software while logged into the dummy account.

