Participants will be compensated for their time and participation in this research; participants may keep the VR headset assigned to them for the study, and will receive a \$50 gift card upon completing the final survey at the end of Week 3. Participants will not be responsible for replacing or repairing the VR device if it is lost or damaged during the study period; a replacement device will be provided by the research team. Participants who wish to return the device may do so at their next scheduled appointment for usual care at MedStar Washington Hospital Center, where a member of the research team will collect it. Participants will not be required to schedule an appointment or return to MWHC for the purpose of returning the device. Participants who wish to return the device and are

unable or unwilling to return to MWHC for any reason will be provided with a prepaid shipping label by mail to return the device to the research team.

Results of this study will be used to determine the effect size, variance and variability to estimate sample size for a larger study. For this pilot study, a sample size of 60 is sufficient to provide accurate estimates of the information needed to calculate sample size for a future study. In the unanticipated circumstance that we are not able to accrue 60 participants during the study period, we will still be able to perform the desired analysis and calculate sample size for a future study if accrual is as low as 30 participants.

Funding for this study has been obtained through the Palliative Care Research Collaborative investigator Development Pilot Award (https://palliativecareresearch.org). The grant award is \$67,031 to support execution of the study over a 1-year period, beginning July 1 of 2022 and ending June 30, 2023.

DATA COLLECTION

Subjects will record daily use of the VR headset and duration of use for each session on a paper calendar provided to them at the time of enrollment. Subject survey data will be collected and entered by the research study coordinator using an online survey system accessible only to the research team (Tonic Health). Subjects will be assigned a de-identified code for survey entry. All data will be password protected and de-identified prior to analysis. Results will be reported in aggregate.

DATA SAFETY MONITORING PLAN

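### The pilot is to supply the effect size for a larger study, but the only pain contrast it yields is an uncontrolled, unblinded change from baseline

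*Combined protocol and SAP*

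**What the plan says.** The sample-size paragraph of Study Design and Methods gives the purpose of the estimates: "Results of this study will be used to determine the effect size, variance and variability to estimate sample size for a larger study". It then says that "a sample size of 60 is sufficient to provide accurate estimates of the information needed to calculate sample size for a future study", and that the team could still run its analysis and "calculate sample size for a future study if accrual is as low as 30 participants".

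The same section states the design: "This is a non-randomized, unblinded dose-titration study". All participants get VR once daily in week 1, twice daily in week 2 and as desired in week 3, on top of their usual analgesia.

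Aim 1 concerns the "impact of a VR intervention against standard care (pre-enrollment analgesic regimen", the parenthesis defining standard care as the patient's own earlier regimen. Hypothesis 1 compares patients with their own baseline. Data Analysis tests the end of each week against baseline (paired t-test or Wilcoxon) and adds a linear mixed model for the trend in pain, adjusted for pain medication and covariates such as age and sex.

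On entry, Aim 1 refers to "outpatients with cancer who have a baseline pain self-rated at least 4/10". The eligibility criteria require that patients "report moderate-severe pain (at least 4 out of 10 where pain is rated on a Likert scale between zero and 10", over the previous 7 days. The recruitment text adds: "The coordinator will screen the electronic health record to confirm eligibility, then schedule a time to meet with the participant". The baseline pain score is collected after consent.

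**The concern.** An effect size used to plan a controlled trial should estimate the difference between treated and untreated patients. This pilot has no untreated patients and no VR-free week. Its change from baseline adds together:

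- any effect of VR;
- the natural course of pain over three weeks, whose direction the documents do not give;
- expectation, because patients who know they are using VR rate their own pain;
- regression to the mean, if patients are selected on the same high rating that serves as baseline.

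The mixed model may absorb some change in analgesic use, but it has no control term and cannot separate the other parts. Contrasts between weeks or levels of use do not help: they are uncontrolled, and the schedule contrast is confounded with time.

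At stake is the size of the next study. If that study is controlled and planned on this change, the error in the effect passes into its sample size.

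**Working it through.** **The plan's own figure.** The documents give no alpha, power, expected effect, SD, correlation, loss rate or precision target. The figures of 60 and 30 therefore cannot be reproduced, and cannot be called wrong. What they deliver for a mean change is a 95% CI half-width, in SD units, of t(0.975, n−1)/√n:

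- n = 60: 2.001/√60 = 0.26 SD
- n = 30: 2.045/√30 = 0.37 SD

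These are for completers. A larger n narrows the interval but does not remove the bias.

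**How large regression to the mean could be.** All inputs are assumptions: no VR effect, no drift, weekly pain mean 4.5, SD 2.2, within-person correlation r = 0.7, entry at 4 or more. On a continuous scale the expected fall is (1−r) × SD × λ, with λ = φ(a)/(1−Φ(a)) and a = (4−4.5)/2.2 = −0.227. So λ = 0.389/0.590 = 0.659, and the fall is 0.3 × 2.2 × 0.659 = 0.43 points. Simulation on a rounded 0–10 scale gives less, mainly because rounding admits underlying values from 3.5. The simulated falls are:

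| Which rating qualifies the patient | Apparent fall (points) |
|---|---|
| The analysed baseline itself | 0.37 (0.06 to 0.73 for means 3.5–6, r 0.6–0.9) |
| Worst pain in the baseline week, assumed 1–2 points above average pain, correlation with it 0.7–0.9 | 0.08 to 0.19 |
| An earlier average-pain rating, correlation decaying (0.7, then 0.49) | 0.24 |
| An earlier average-pain rating, equal correlation | 0 |

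In the first row, SD 1.5 gives 0.22 and SD 3 gives 0.55. The answer depends on which rating is the baseline. Aim 1 implies that it is the qualifying one. The eligibility, screening and baseline-assessment texts leave room for a separate, earlier rating.

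**Effect on a later two-arm study.** Further assumptions: two-sided 5%, planned power 80%, true VR effect δ, and a planning effect δ + b, where b is the overstatement. The SD is taken as correctly known, so it cancels. With D = (δ + b)/δ, the planned n is 1/D² of the n required, and true power is Φ(2.802/D − 1.960).

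| δ | b | D | n planned / n required | True power |
|---|---|---|---|---|
| 1 | 0 | 1.00 | 1.00 | 80% |
| 1 | 0.08 | 1.08 | 0.86 | 74% |
| 1 | 0.24 | 1.24 | 0.65 | 62% |
| 1 | 0.37 | 1.37 | 0.53 | 53% |
| 1 | −0.24 | 0.76 | 1.73 | 96% |
| 0.5 | 0.24 | 1.48 | 0.46 | 47% |
| 2 | 0.24 | 1.12 | 0.80 | 71% |

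The positive values of b come from regression to the mean alone. Expectation could add to them, and natural course could move the total either way. The row with b = −0.24 stands for worsening that hides part of the effect.

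**The case against.** The design is openly described as non-randomized and unblinded, Aim 1 calls its results pilot data, and Hypothesis 1 names baseline as the comparator. The protocol defends self-reported pain as the standard outcome. The sample-size paragraph says effect size, not VR effect, and does not say that the change will be used undiscounted or as a difference between arms. The larger study's design is not given, and a larger single-arm study would need this same before-after quantity. Nothing in the present study's procedures or tests would change. All of this stands, and it limits the point to the use made of the estimate.

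It does not remove the point. Effect size is listed first and without qualification among the quantities to carry forward, and no other comparator for pain is offered. Self-report as such is not the fault; the issue is that participants know they are receiving VR.

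A reader might also infer that the pilot is bound to flatter VR. The documents do not support that. Regression to the mean may be small or absent if a separate earlier rating qualifies patients, and worsening pain would push the other way. Nor do they call 30 participants accurate: that word is applied to 60 only, and 30 is described as still workable.

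**Conclusion.** The concern holds as a matter of how the pilot's result is to be used. Following the sample-size paragraph would carry forward, as the effect size, a change whose non-VR part has unknown size and direction. Harm follows if the later study is controlled and adopts that change. On the assumed inputs, with a true effect of 1 point, power ranges from 80% with no overstatement to 53% with 0.37 points. For an overstatement of 0.24 points, it ranges from 47% to 71% for true effects of 0.5 to 2 points. These percentages are illustrations, not properties of this plan.

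It would go too far to conclude that a single-arm pilot is the wrong design or that 60 is the wrong number. The pilot can reasonably supply the SD and the within-person correlation, with the caveat that the SD of change may differ in a control arm. The correction should be made, but it does not threaten the conduct of this study.

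**What to change.** **Main change, in the sample-size paragraph.** State that the larger study will be sized from a prespecified clinically important between-group difference and from this pilot's SD and within-person correlation at a week named in advance. State that uncertainty in the SD will be allowed for, for example by an upper confidence limit, and that the SD of change may differ in a control arm. State that the observed mean change will not be used as the VR effect size. The week must be named because each week has a different VR schedule.

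**Cost.** The difference and the week must be chosen before data are seen, and the later sample grows. With a one-sided 80% upper limit for the SD, the factor is (n−1)/χ²(0.20, n−1): 59/49.72 = 1.19 at 60 completers and 29/22.48 = 1.29 at 30. This study needs no added participants, visits or arms.

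**Secondary wording.**

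- Give the precision behind the claim of accuracy for 60 (half-width 0.26 SD), and for the fallback of 30 (0.37 SD).
- Describe Aim 1 results as an uncontrolled change from the pre-enrollment baseline.
- Reconcile Aim 1, the eligibility and screening text, and the baseline assessment text on whether the qualifying rating is the analysed baseline.
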